C.1. Study design. This is a double-blind, 4-intervention, 4-period crossover randomized controlled trial of HFOx, HFAir, LFOx, and LFAir in non-hypoxemic cancer patients (**Figure 3**). We plan to enroll 36 patients in total. The eligibility criteria are listed in **Table 1**. We will use a computer-generated sequence for randomization. Even with 2 different flow rates, patients and research staff will be blinded to the gas (i.e., oxygen v. air) while a separate respiratory therapist will provide the study intervention; thus, this will remain a double-blind study. On the basis of our experience conducting symptom control trials, we believe this study design will not be an undue burden for hospitalized patients (approximately 1-2 hours, including washout).¹⁹ The rationale for the current study design is as follows:

[figure not shown]

Figure 3. Study Flow Chart. In this double-blind, 4-intervention, 4-period crossover randomized controlled trial, all patients will try 10 minutes of each intervention, followed by a variable washout period (purple arrow). The sequences above represent one of the 6 Latin Squares that may be used.

- **Crossover design**—This design allows intra-individual comparison, thus maximizing study power (144 tests in 36 patients) in addition to providing overall preference.²⁰ We use the Latin square design to minimize the sequences needed.
- **Intervention duration**—We will limit this intervention to only 10 minutes in this proof-of-concept study to minimize study burden and attrition, and to examine the effect of short intervention. We expect the effect of gas exchange to be rapid. Previous dyspnea studies with oxygen delivery have utilized similar durations⁸.
- **Variable washout period**—although the washout period is expected to be short (<10 min), it has not been defined. Thus, we will measure dyspnea on the Numeric Rating Scale starting after 10 minutes of each intervention every 5 minutes until patient returns to within 1 point of the baseline level of dyspnea (i.e. immediately prior to starting the first intervention) before we proceed to the next intervention.
- **Inclusion of HFOx, HFAir and LFAir arms**—HFOx has not been tested in non-hypoxemic cancer patients. No published study has examined the therapeutic role of HFAir in any patient population. The efficacy of LFAir has not been studied in the hospitalized population²¹.

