⁴ Heart rate, respiratory rate, oxygen saturation, and transcutaneous CO₂ level will be measured.

⁵ Dry eyes, dry nose, nasal moisture and anxiety will be assessed using a numeric rating scale from 0 (not at all) to 10 (worst possible).

⁶ Dyspnea intensity will be assessed using the NRS scale every 5 minutes until patients return to baseline. The duration of washout is a useful secondary outcome.

⁷ FiO₂, flow rate, and temperature.

⁸ We will assess blinding (oxygen v. air) of patients and research staff after each treatment. At the end of the study, patients will be asked which of the 4 interventions they prefer

D. STATISTICAL CONSIDERATIONS

D.1. Analysis plan.

Design: We propose a 4-period, 4-intervention balanced Latin-square cross-over (Williams) design with 4 sequences and 36 patients (i.e., 9 replicates per sequence). The primary outcome is the Dyspnea Numeric Rating Scale (0-10). Each intervention is 10-minutes long with NRS assessments at 0, 5 and 10 minutes. Washout periods between interventions will continue until NRS assessment returns to within one unit of baseline.

Primary analysis: We will fit a mixed effects linear model to the Dyspnea Numeric Rating Scale data to account for the repeated measurements (i.e. 0, 5 and 10 minutes) which yield period, sequence, and carryover effects and to model the various inter-patient and intra-patient sources of variation. Appropriate data visualization and residual analyses will also be performed. The primary objective of the study is to obtain preliminary estimates of the effect sizes (In a mixed model, the slope of change will provide an estimate of effect size. We will also determine the mean change in NRS over 10 minutes for each study intervention).

Secondary analysis #1: We will estimate the completion rate as the proportion of patients starting treatment that complete all four interventions.

Additional secondary analyses: Using mixed effects linear models we will obtain preliminary estimates of the study effects for physiologic function (oxygen saturation, respiratory rate, transcutaneous CO₂). We will also assess washout period duration in a similar fashion. Finally, we will tabulate patient intervention preferences obtained at the end of the study.

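### Does D.1 need to say whether carryover acts on the 0-10 minute slope and the mean change, and not only on the NRS level?

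*Combined protocol and SAP*

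**What the plan says.** The primary analysis in D.1 is a linear mixed model for NRS "to account for the repeated measurements (i.e. 0, 5 and 10 minutes) which yield period, sequence, and carryover effects". Two effect sizes follow: "In a mixed model, the slope of change will provide an estimate of effect size", and "We will also determine the mean change in NRS over 10 minutes for each study intervention". Neither the order nor the form of the carryover term is given, and no carryover adjustment is mentioned for the mean change.

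On washout, D.1 states: "Washout periods between interventions will continue until NRS assessment returns to within one unit of baseline". C.1 has the same tolerance ("until patient returns to within 1 point of the baseline level of dyspnea"), and so does C.11. Note 6 to Table 2 is shorter: "Dyspnea intensity will be assessed using the NRS scale every 5 minutes until patients return to baseline". C.1 adds that "although the washout period is expected to be short (<10 min), it has not been defined".

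The design in D.1 is a Williams square with 4 sequences and 9 patients on each. The Figure 3 legend says: "The sequences above represent one of the 6 Latin Squares that may be used". A.1 asks for preliminary estimates of effect size.

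**The concern.** Both effect sizes are most naturally measured from each period's own 0-minute score. If an arm leaves some relief behind and that relief fades during the next 10 minutes, the NRS rises for a reason unrelated to the gas then being given. In a Williams square an arm never follows itself. An arm that leaves more fading relief therefore contaminates its comparators and not itself, and looks better than it is.

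B.3 suggests that high flow may act for some time, so an analyst might expect the error to favour the working hypothesis. A carryover term that shifts only the level may leave the slope untouched, while a reader of D.1 could take the slope as carryover-adjusted. The effect sizes are the trial's main product, and this bias does not shrink with more patients.

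**Working it through.** The plan gives no figure for carryover, so there is none to reproduce. The only interval in D.2 concerns the completion rate and does not bear on this point.

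**1. The two effect sizes coincide.** With readings at 0, 5 and 10 minutes, the least-squares slope is (-5·NRS0 + 5·NRS10)/50 = (NRS10 - NRS0)/10. Ten times the slope is the 10-minute change, so both carry the same bias.

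**2. Size of the bias.** Let arm a leave mean residual relief c_a at the next 0-minute reading, and let a fraction f_a fade within 10 minutes. Each arm is first once and follows every other arm once. With S the sum of f·c over the four arms, the mean change in arm a is raised by (S - f_a·c_a)/4. Hence

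bias(a - b) = -(f_a·c_a - f_b·c_b)/4,

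and the same form holds for pooled high minus low flow. It holds in all 6 Williams squares with complete data.

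- c_H = 0.5, c_L = 0, f = 0.5: -0.25/4 = -0.06.
- c_H = 1, c_L = 0, f = 1: -0.25. This needs a full point left after high flow, none after low flow, and complete fading.
- Equal residuals of 0.5, f_H = 0.2, f_L = 0.8: -(0.10 - 0.40)/4 = +0.075. The sign reverses although the 0-minute scores do not differ.

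**3. What a level-only term does.** Least squares with a true contrast of -1.00 and c_H = 1, c_L = 0, f = 1 gives:

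| Model | Estimate |
|---|---|
| Level-only carryover, treatment intercepts | -1.25 |
| Level-only carryover, shared intercept | -1.106 |
| Carryover and period each interacting with time | -1.00 |

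The shared intercept removes (0.25 - 0.106)/0.25 = 58% of the bias. The result depends on choices that D.1 leaves open.

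**4. Plausible size.** The documents give neither residuals nor fading rates, so these are assumptions. Applying the washout rule with high-flow relief 1.0 or 1.9, low-flow relief 0 to 1, half-life 2.5 to 40 minutes and SD 1 to 2.5:

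| Assumed set-up gap | Range of bias | Median |
|---|---|---|
| none | -0.18 to -0.01 | -0.05 |
| 5 min | -0.10 to -0.01 | -0.03 |
| 10 min | -0.07 to 0.00 | -0.02 |

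Some gap is likely, because C.6 has staff leave the room while the device is set up. These inputs never let low-flow relief exceed high-flow relief, so the sign is largely built in. A full-trial simulation with the 0-10 scale limits (720 scenarios, 1,000 runs each, n = 36) gave -0.18 to +0.12, median -0.02.

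**5. Against the standard error.** B.3 reports a mean change of 1.9 (95% CI 0.4 to 3.4), a half-width of 1.5. The implied SD is 1.5·√13/2.179 = 2.5 if n = 13, or 1.5·√15/2.145 = 2.7 if n = 15. With SD 2.5, 36 patients and within-patient correlation ρ of the changes, the SE of high minus low flow is 2.5·√(1 - ρ)/6. That is 0.42 at ρ = 0 and 0.19 at ρ = 0.8. Median biases of 0.02 to 0.05 are 0.02/0.42 = 5% to 0.05/0.19 = 26% of one SE. The largest simulated value, 0.18, is 43% to 95% of one SE.

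**6. Does adjustment gain?** First-order carryover on the change multiplies the SE by 1.049 and the variance by 1.10. It lowers mean squared error only if the bias exceeds √0.10 = 0.32 SE, that is 0.06 to 0.13 point. In the 720 scenarios it lowered root mean squared error in 15% (ratio 0.75 to 1.12, median 1.03): 32%, 11% and 2% at gaps of 0, 5 and 10 minutes. Adding the 0-minute NRS as well lowered it in 84% (median ratio 0.94), but at half-lives of 20 to 40 minutes that estimate can understate the contrast by up to 0.23.

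**The case for a change.** The best case for a change is that it costs a sentence. All the readings are already collected, D.1 is the whole analysis plan, and one ordinary reading of it (level-only carryover with treatment intercepts) does nothing for the slope. If high flow leaves more fading relief, the error flatters the hypothesis. Each arm's mean change is also blunted: a common residual of 0.5 with a 5-minute half-life costs 0.75 × 0.5 × 0.75 = 0.28 point.

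Some of this stands. D.1 is silent on the form, and the algebra is right. The rest is weaker:

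- The direction is not established. B.3's evidence of persistence is two patients. The 1.9-point change came from two-hour sessions in a trial population that was 93% hypoxemic; here sessions last 10 minutes in non-hypoxemic patients. Relief that persists fades little within 10 minutes, so it causes little bias.
- The persistent case raised in B.3 is also where the fuller adjustment does worst.
- Comparing 0-minute scores by preceding arm is a useful description but not a safe bound, as the +0.075 example shows.
- The per-arm blunting is not cured by a carryover term when period-by-time effects are fitted. The per-arm mean change reads as a descriptive summary in any case.

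**Conclusion.** The gap in wording is real, but it is missing detail and not a shown error. D.1 commits to no level-only term. An analyst who takes the slope as the effect, and so lets treatment interact with time, can enter carryover the same way and see its influence from data already collected.

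The likely distortion is small for a trial of 36 patients seeking preliminary estimates: a median of 0.02 to 0.05 point, of either sign once low flow may leave as much fading relief as high flow, against an SE of 0.19 to 0.42. Whether to adjust is a trade of bias for variance on which statisticians would differ, and under most assumed inputs carryover alone does slightly worse. These sizes rest on assumed relief, half-lives, set-up gap and correlations, and on Williams balance with complete data. A differential near 1 point with rapid fading would give up to 0.25, but that needs a near-extreme combination.

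Note 6 to Table 2 differs from the one-point tolerance in C.1, C.11 and D.1. It is most easily read as shorthand. The passages must be reconciled as a clerical matter, and the conclusion here does not depend on it.

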High-Flow Oxygen for Dyspnea in Hospitalized Cancer Patients

Principal Investigator: [name]

Co-Chair: [name]

Collaborators: [name], [name], [name], [name], [name], RT, [name], [name], [name]

Funding source: This study is supported by the Sabin Family Fellowship Award (P.I. [name]). The funding for this study starts March 1, 2016.

A. STUDY OBJECTIVES

A.1. Primary Objective. Obtain preliminary estimates of the effect size of high flow oxygen and air on dyspnea. Our working hypothesis is that high flow oxygen/air will be associated with lower levels of dyspnea than low flow oxygen/air in cancer patients.

A.2. Secondary Aim #1. Determine the completion rate of a randomized controlled trial of dyspnea in cancer patients. Our working hypothesis is that at least 80% of patients will complete the 4 periods of this study.

A.3. Secondary Aim #2. Obtain preliminary estimates of the effects of high flow oxygen and air on physiologic function (oxygen saturation, respiratory rate, transcutaneous CO₂). Our working hypothesis is that high flow oxygen and air will improve physiologic function.

B. BACKGROUND AND SIGNIFICANCE

B.1. Dyspnea is defined as “a subjective experience of breathing discomfort that consists of qualitatively distinct sensations that vary in intensity”¹. It occurs in approximately 10%-70% of cancer patients and is one of the most feared symptoms^{2, 3}. More than 80% of patients with dyspnea have breakthrough episodes, particularly with physical exertion⁴. Dyspnea is associated with decreased function, quality of life, and survival⁵. The pathophysiological features of dyspnea are shown in Figure 1. The sensory cortex receives afferent input from various peripheral and central stimuli, generating the sensation of breathlessness^{1, 6}. Parenchymal metastasis, lymphangitic carcinomatosis, airway obstruction, pleural effusion, pneumonia, pulmonary embolism, and atelectasis may cause difficulty breathing in the context of progressive cancer.

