randomized controlled trial comparing HFOx and bilevel positive airway pressure (two hours each) in advanced cancer patients with refractory dyspnea. Twenty-four of 30 (80%) patients completed the study interventions, suggesting that a study of these two devices is feasible in this patient population. HFOx (mean change, 1.9; 95% CI, 0.4-3.4; $P=0.02$) was associated with significant improvements in dyspnea (Figure 2). Remarkably, two patients who completed HFOx reported low dyspnea scores (≤ 2 of 10) up to 1 hour after discontinuing use of the devices. This observation is of particular interest because the mechanical effect of HFOx on breathing effort may have a long-lasting effect on dyspnea. Overall, 10 of 13 (77%) patients who completed HFOx reported dyspnea improvement, with none experiencing significant adverse effects. Of note, this study was conducted in patients who were predominantly hypoxemic (93%) and did not respond to LFOx. These data support the feasibility of conducting a clinical trial with HFOx in cancer patients and provide preliminary evidence of its efficacy. Importantly, HFOx and HFAir have not been formally tested in non-hypoxemic patients, which is why the proposed trial is particularly novel.

[figure not shown]

Figure 2. Improvement in Dyspnea Before and after high flow oxygen (N=15)

B.4. Low-flow supplemental oxygen for non-hypoxemic cancer patients¹⁸. In a double-blind, randomized trial, we found that LFOx at 5 L/min did not improve dyspnea during a 6-minute walk compared with LFAir at 5 L/min. The results of this important

study highlight the lack of efficacy of LFOx for dyspnea in non-hypoxemic patients and the need to evaluate novel treatment options (i.e., HFOx and HFAir).

B.5. Study rationale. We expect to advance our understanding of how HFOx can be used to treat dyspnea in non-hypoxemic cancer patients. The effective management of dyspnea may ultimately help alleviate this devastating symptom. By elegantly dissecting the high-flow mechanism from the oxygen content and capturing changes in physiologic parameters, we will gain a better understanding of the mechanisms that help alleviate dyspnea and devise newer, more effective treatments.

C. RESEARCH DESIGN AND METHODS

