- **Use of LFAir as control**—LFAir at 2 L/min is a well-accepted control intervention in published studies.

C.2. Eligibility criteria. The eligibility criteria are shown in Table 1. The rationale for including patients with obstructive and restrictive lung disease in this study is that the mechanisms of dyspnea relief (e.g., trigeminal nerve stimulation and decreased breathing effort; see Figure 1) are applicable to both types of pulmonary disorder.

Table 1. Study Eligibility Criteria

Inclusion Criteria

1. Diagnosis of cancer
2. Patients seen by palliative care, thoracic oncology, pulmonary medicine, or emergency care at MD Anderson Cancer Center
3. Dyspnea Numeric Rating Scale at rest ≥ 3 of 10 (average over last 24 hour)
4. Non-hypoxemic (i.e. oxygen saturation $>90\%$ on ambient air)
5. Able to communicate in English or Spanish
6. Age ≥ 18 years
7. Able to tolerate high-flow oxygen/air

Exclusion Criteria

1. Memorial Delirium Rating Scale >13
 2. Hemodynamic instability
 3. Respiratory failure requiring mechanical ventilation or non-invasive ventilation
 4. Frequent use of rescue opioids $>8x/day$ or rescue bronchodilators $>8x/day$ over last 24 hours
 5. Currently requiring high flow oxygen for oxygenation
-

C.3. Recruitment. Patients seen by the supportive care team, thoracic oncology, pulmonary medicine, or emergency care will be screened for this study. The supportive care inpatient consultation team sees 80 patients (10-20 new consults) per day. A two-step consent process will be used. First, verbal consent will be obtained by the study staff before screening potential participants to determine their eligibility. Before signing any consent document, a respiratory care therapist will allow patients a trial of high-flow oxygen/air to ensure tolerance of high flow. Eligible patients will be formally enrolled in the study after they have signed the informed consent form indicating their willingness to participate in the trial. Once enrolled, the research staff will work with the patient to identify ideal time to conduct the study. We will document the number of patients who are screened, approached, eligible, enrolled, and randomized for the study and the number who complete it. When patients complete study procedures, they will be compensated with a \$25 gift card as a show of appreciation for their time and participation. Patients' reasons for declining to participate will also be captured.

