C.6. Blinding. The patients and research staff will be blinded to the assignment of the gas (i.e., oxygen vs. air). The gas will be delivered via gas outlets inside the patient's room, located behind the bed. Only the respiratory therapist administering the gas will be aware of its identity. To ensure proper blinding, the research staff will step out of the room while the respiratory therapist sets up the gas delivery device. The gas supply will be covered with a piece of cloth to ensure proper concealment. The respiratory care specialist will be specifically asked to not to discuss the identity of the study gas. We will assess blinding by asking the patients and study staff about the identity of the gas at the end of study. The flow rate cannot be blinded in this study.

C.7. Study outcomes. See Table 2 for a detailed description of the study assessments. We will also collect data on patient demographics and study feasibility outcomes (rates of enrollment and attrition). The study interventions will be provided to patients while at rest, and dyspnea ratings will only be assessed when patients are at rest.

C.8. Co-interventions. We expect that co-interventions will be minimal because of the short study period. We will document any regularly scheduled, bronchodilators or opioids given 1 hour before or during the study period. However, if patients required as need opioids (for pain or any other reasons) or bronchodilators during the study period, they will need to come off study and will need to be replaced.

C.9. Training of research staff. An orientation will be held with all research staff involved in this study to introduce them to the study design and standardize the provision of each intervention. Particular attention will be paid to ensuring that research staff provide patients with proper instructions so they understand the study assessments. We will also have several mock-ups for practicing the study procedures.

C.10. Data Safety Monitoring Board (DSMB). The MD Anderson DSMB will be providing monitoring for patient safety and data quality assurance purposes.

C.11. Dropouts. Patients will come off study if (1) they decide for any reason to stop; (2) they did not achieve within 1 point of the baseline level of dyspnea after 1 hour during the washout period, (3) they require as need opioids (for pain or any other reasons) or bronchodilators during the study period. These individuals will need to be replaced.

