D.2. Sample size justification. We will enroll 36 patients over 2 years. Although due to the complexity of the statistical models we cannot accurately estimate the precision of our effect estimates, based on our experience with mixed effects models, 36 patients with 12 repeated measurements (3 times for each of 4 interventions) will provide adequate precision. If the completion rate is 80% then with 36 patients, a 95% confidence interval on this estimate would extend from 64% to 92%.

E. DATA CONFIDENTIALITY PROCEDURES

Study data will be collected and managed using REDCap (Research Electronic Data Capture) tools hosted at MD Anderson or hardcopy surveys. Participants will have the option to complete surveys electronically or hardcopy. Data entry of any hardcopy survey will be completed using REDCap software. REDCap (www.project-redcap.org) is a secure, web-based application with controlled access designed to support data capture for research studies, providing: 1) an intuitive interface for validated data entry; 2) audit trails for tracking data manipulation and export procedures; 3) automated export procedures for seamless downloads to common statistical packages; and 4) procedures for importing data from external sources. In the case of multi-center studies REDCap uses Data Access Groups (DAGs) to ensure that personnel at each institution are blinded to the data from other institutions. REDCap (<https://redcap.mdanderson.org>) is hosted on a secure server by MD Anderson Cancer Center's Department of Research Information Systems & Technology Services.

REDCap has undergone a Governance Risk & Compliance Assessment (05/14/14) by MD Anderson's Information Security Office and found to be compliant with HIPAA, Texas Administrative Codes 202-203, University of Texas Policy 165, federal regulations outlined in 21CFR Part 11, and UTMDACC Institutional Policy #ADM0335. Those having access to the data file include the study PI and research team personnel. Users are authenticated against MDACC's Active Directory system. All protected health information (PHI) will be removed from the data when it is exported from REDCap for analysis. Following publication study data will be archived in REDCap.

Health information will be protected and we will maintain the confidentiality of the data obtained from the patient's chart.

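### The effect size named in D.1 is a within-intervention change, while A.1 asks about high versus low flow; the contrast and its confidence interval should be named

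*Combined protocol and SAP*

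**What the plan says.** The A.1 objective is to estimate the effect size of high flow oxygen and air on dyspnea. Its working hypothesis is comparative: "high flow oxygen/air will be associated with lower levels of dyspnea than low flow oxygen/air in cancer patients". Other sections point the same way. B.5 describes the purpose as "By elegantly dissecting the high-flow mechanism from the oxygen content". C.1 justifies the crossover with "This design allows intra-individual comparison, thus maximizing study power (144 tests in 36 patients" and names the reference arm: "LFAir at 2 L/min is a well-accepted control intervention in published studies".

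D.1 (Primary analysis) plans a mixed effects linear model for the NRS at 0, 5 and 10 minutes and mentions period, sequence and carryover effects. It then says what the effect size will be: "In a mixed model, the slope of change will provide an estimate of effect size", followed by "We will also determine the mean change in NRS over 10 minutes for each study intervention". D.1 names no contrast between interventions and no confidence interval for one, and no other section supplies either. D.2 states that "we cannot accurately estimate the precision of our effect estimates"; the only interval it gives is for the completion rate.

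**The concern.** The effect size is the main product of this trial, so its definition should match the comparison in A.1. The second measure in D.1 is a before-after change within one intervention. The first is a slope that could be either a per-intervention slope or a difference in slopes.

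A before-after change over 10 minutes at rest contains whatever happens over time, the placebo response to a nasal device and gas flow, and the patient's expectation. All four interventions can therefore show a fall when flow has no effect. The flow effect is the difference between interventions in the same patient, which is why a crossover was chosen. If D.1 is followed literally, the trial could report four changes and leave the comparison in A.1, with its within-patient precision, unreported.

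**Working it through.** **Plan's own figure.** The documents give no figure for the primary effect or its precision. The only interval in D.2 (64% to 92% for 80% completion) reproduces as an exact interval for 29 of 36 (64.0% to 91.8%) and is not in dispute.

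**1. What each reading of D.1 delivers** (invented changes, for illustration)

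| 10-minute NRS change | Slope per minute, high-flow arms | Slope per minute, low-flow arms | High minus low, change | High minus low, slope |
|---|---|---|---|---|
| −2 in both high-flow arms, −1 in both low-flow arms | −0.20 | −0.10 | −1.0 | −0.10 |
| −1.5 in every arm | −0.15 | −0.15 | 0 | 0 |

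In the second row every arm improves by 1.5 points and the flow effect is 0. Only the difference columns answer A.1.

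**2. Interval a reader could build from arm summaries.** Let τ be the SD of the 10-minute change and ρ the correlation of a patient's changes across periods; both are assumptions. The flow contrast is (HFOx + HFAir)/2 − (LFOx + LFAir)/2. Treating the arms as independent with 36 patients:

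SE = τ × √(4 × (1/4)/36) = τ/6 = 0.1667τ.

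**3. Within-patient interval.** The inputs from D.1 are the Williams square, 4 sequences and 9 patients per sequence. With patient, period, intervention and first-order carryover effects, one change score per period, and within-patient SD σ = τ√(1 − ρ), least squares gives:

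- flow contrast: SE = 0.1748σ
- one pair of interventions: SE = 0.2472σ
- degrees of freedom: 144 − 36 − 9 = 99, so t = 1.984

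Without carryover terms the flow SE would be σ/6 = 0.1667σ. The adjustment raises the variance by (0.1748/0.1667)² ≈ 1.10.

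**4. Width ratio, independent-arm over within-patient** = (1/6) / (0.1748 × √(1 − ρ))

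| ρ (assumed) | 0 | 0.1 | 0.2 | 0.3 | 0.5 | 0.7 |
|---|---|---|---|---|---|---|
| Ratio | 0.95 | 1.01 | 1.07 | 1.14 | 1.35 | 1.74 |

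For τ = 2.0 the independent-arm half-width is about 0.66 NRS points, against 0.58, 0.49 and 0.38 at ρ = 0.3, 0.5 and 0.7. In simulation (4,000 trials per correlation, no flow effect) the independent-arm interval covered 97.8%, 99.4% and 99.9% of the time, and the within-patient interval about 95%.

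**5. Precision of the contrasts** (95% half-width, NRS points, carryover-adjusted)

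With 28 patients (7 per sequence, the balanced number just under 80% of 36 = 28.8), the flow SE is 0.1748 × √(36/28) = 0.1982σ on 112 − 28 − 9 = 75 df, t = 1.992.

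| σ (assumed) | 1.0 | 1.5 | 2.0 | 2.5 |
|---|---|---|---|---|
| Flow, 36 completers | 0.35 | 0.52 | 0.69 | 0.87 |
| Flow, 28 completers | 0.39 | 0.59 | 0.79 | 0.99 |
| HFOx − LFOx or HFAir − LFAir, 36 completers | 0.49 | 0.74 | 0.98 | 1.23 |

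Example: 1.984 × 0.1748 × 2.5 = 0.87.

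Fitting the 0-, 5- and 10-minute NRS as responses, with intervention-by-time terms, gives a flow SE of 0.1741σ to 0.1748σ. The half-widths therefore carry over to the model that D.1 plans.

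**The case against.** The strongest defence has four parts.

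- **The model already contains the answer.** A four-intervention crossover with carryover terms implies intervention effects, and differences follow directly from an intervention-by-time model. This stands: the gap is in the effect size that D.1 names, not in the design, the data or the model. A reader might infer that the trial cannot estimate the flow effect, and the documents do not support that.
- **The slope is not one pooled number.** A reader might infer a single slope across all four arms, which would say nothing about flow. D.1 speaks of effect sizes in the plural and of each intervention, so that reading is strained. The real ambiguity is between per-intervention slopes and differences in slopes.
- **The arm means can be subtracted.** They can, which gives the point difference. A reader might infer that no valid interval for it would exist. That is too strong: the independent-arm interval is conservative, and at a correlation of about 0.1 or less nothing material is lost. Nor does D.1 say that intervals will be withheld.
- **It is a proof-of-concept study, and the comparison is only a working hypothesis.** No test or power is being asked for. But a preliminary estimate still has to estimate the quantity in question, and a before-after change does not isolate what high flow adds.

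A.1 does not settle whether flow should be averaged over gas or compared within each gas. Reporting the averaged contrast with the two within-gas contrasts beside it covers both.

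**Conclusion.** The point holds. D.1 names a within-intervention measure, and a slope of unstated type, as the effect size for a comparative hypothesis, and commits to no between-intervention contrast or interval. It should be corrected, though it does not threaten the trial: the planned model and data can answer A.1.

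The cost in precision depends on a correlation that the documents do not give. It is about nil at 0.1 and reaches 1.74 times the interval width at 0.7. The half-widths also rest on assumed SDs, on balanced completion of all four periods and on first-order carryover terms. The earlier result in B.3 does not fix the SD: it is a change after two hours of treatment, in mostly hypoxemic patients. The mismatch between A.1 and D.1 needs none of these assumptions.

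Naming the contrast does not remove every bias. C.6 states "The flow rate cannot be blinded in this study", so expectation tied to flow itself stays in the high-versus-low comparison.

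**What to change.** In D.1, replace the definition of effect size along these lines: the primary effect size is the difference in 10-minute NRS change (or in slope; choose one) between high and low flow, averaged over gas, (HFOx + HFAir)/2 − (LFOx + LFAir)/2, with a 95% CI. It is estimated from the planned mixed model with an intervention-by-time term alongside the period, sequence and carryover terms, and negative values favour high flow. Report HFOx − LFOx and HFAir − LFAir with CIs beside it. Keep per-arm slopes and mean changes as descriptive.

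Optionally, add to D.2 that the 95% half-width of the flow contrast would be about 0.35 to 0.87 NRS points with 36 completers, or about 0.39 to 0.99 with 28, for an assumed within-patient SD of change of 1.0 to 2.5. Label the SD as an assumption.

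The cost is a few sentences. The 0-, 5- and 10-minute ratings are already collected in every period, so no new patients, visits or measurements are needed.
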